### Phase I/II Study of the Combination of Panobinostat and Carfilzomib in Patients with Relapsed/Refractory Multiple Myeloma

Amd #	Amd Date	Revision(s) Made	Refer to this Section in the Protocol
1	27 September 2011	
Exclusion criteria added, "Patient has not recovered from all therapy-related toxicities associated with prior treatments to < Grade 2 CTCAE."
 
Section referring to panobinostat dose modifications for prolonged QTc interval has been modified to remove all references to centralized readings of ECGs by Novartis.
 
All cardiac events should be treated according to standards and referred to a specialist if clinically indicated. Treatment decisions at the sites will be based on QTc as determined by the automated machine reading (or as measured and calculated by trained personnel at the site). <del>The centralized readings of ECGs by eRT will use the Fridericia correction: QTcR. Any final decisions concerning any dose modifications or patients discontinuing study drug permanently will be based on QTcF calculations assessed by eRT and evaluated via a discussion between the Study Chair.</del> If a patient
 
References to transmit ECGs in Table 6: Criteria for Dose Reductions, Delays and/or Re-Institution Due to Drug-Related QTcF Abnormalities have been struck.
 
Modifications to the Section - General Monitoring Principals
 
#7. All ECGs will be reviewed by the treating physician prior to administering the dose of panobinostat. <del>If the QTc interval is > 480 msec, the ECG will be sent to eRT and the SCRI Study Chair via SCRI ORC facsimile for review.</del>
 
<del>#11 Two ECG paper tracings will be printed each time an ECG is performed. One original will remain with the source documentation. The second original will be stored for submission to eRT at the end of each treatment cycle.</del>
	
 
• Synopsis, Section 3.2 Exclusion Criteria #4
 
• Section 6.2
 
• Table 6
 
• Section 6.2.1
 

## History of Amendments for MM 27 (continued)

Amd #	Amd Date	Revision(s) Made	Refer to this Section in the Protocol
1	27 September 2011	If any QTc interval is $\geq 500$ msec, the patient must have at a minimum, hourly ECG monitoring until the QTc is $< 480$ msec. In addition to the minimum hourly ECG monitoring, telemetry monitoring is strongly recommended. <del>ECGs must be transmitted to the Sponsor for prompt review.</del> Prior to a patient with a QTc interval $> 500$ msec being discharged to home, that patient must have at least 2 consecutive, hourly ECGs obtained at least 6 hours after dosing that demonstrate a QTc interval of $\leq 480$ msec.	

• Section 6.2.1

## History of Amendments for MM 27 (continued)

Amd #	Amd Date	Revision(s) Made	Refer to this Section in the Protocol
2	19 July 2012	
As of December 31, <del>2008</del>, 2010 <del>twenty-two</del> 32 clinical studies, including clinical pharmacology, phase I and/or phase II, have either been completed or are ongoing. A total of <del>789</del> 1589 patients were enrolled and received at least one dose of panobinostat.
 
2) Patients must have measurable disease requiring systemic therapy defined as at least one of the following:
 
 
• Serum M-protein <math>\geq 4</math> <del>0.5</del> 0.5 g/dl (<math>\geq 40</math> <del>5</del> 5 g/l)
 
• Urine M-protein <math>\geq 200</math> mg/24 hrs
 
 
Serum free light chain assay: involved free light chain level <math>\geq 10</math> mg/dl (<math>\geq 100</math> mg/l) provided the serum free light chain ratio is abnormal
 
A maximum of <del>three</del> four dose levels will be evaluated.
 
Cycle 2 —<del>12</del> and beyond
 
Phase I Dose Level 3 Cycle 1, Carfilzomib dose is <del>36</del> 45 mg/m^2 IV D8, 9 15, 16
 
Phase I Dose Level 4 Cycle 1, Carfilzomib dose is <del>36</del> 45 mg/m^2 IV D8, 9 15, 16
 
 
• CrCl changes are mostly transient, reversible, and non-cumulative. All patients should be well hydrated. Clinically significant electrolyte abnormalities should be corrected prior to dosing with carfilzomib. Renal function must be monitored closely during treatment with carfilzomib. Serum chemistry values, including creatinine, <del>must be obtained</del> are strongly encouraged and reviewed prior to each dose of carfilzomib during Cycles 1 and 2. The decision will be at the discretion of the treating physician. Carfilzomib must be held for subjects with a CrCl < 15 mL/min at any time during study participation.
 
 
All patients must have the following assessments performed before receiving their first dose of protocol therapy (labs may be obtained up to 72 hours prior to treatment):
 
The physical examination, <del>complete blood counts</del> CBCs, CMP, uric acid and pregnancy test should be done <7 days prior to initiation of treatment.
	
 
• Section 1.2.1
 
• Synopsis, Section 3.1, #2
 
• Synopsis, Section 5,
 
• Section 5.1, Table 1
 
• Section 5.2, Table 2
 
• Section 6.4
 
• Section 7.2
 


Amd #	Amd Date	Revision(s) Made	Refer to this Section in the Protocol
2	19 July 2012	
 
• CBC, 3-part differential and platelets (-3 to Day 1 window allowed)
 
• CMP (see Section 7.1.) plus magnesium and phosphorus (-3 to Day 1 window allowed)
 
• Uric acid (if clinically indicated) (-3 to Day 1 window allowed)
 
• Vital signs (blood pressure, weight, pulse, and respiratory rate)
 
• Measurement of vital signs (blood pressure, pulse, and respiratory rate and weight) (Day 1 only)
 
 
Re-Staging – 4 Weeks (-7 to Day 1 window allowed)
 
At any point in this treatment, patients suspected of PD will have response assessed again to confirm disease progression (i.e. 2 sets of response assessments at least 1 week apart). The outcomes will be reviewed by the study chair before the patient is removed from the study.
 
MR – Minimal Response
 
Minimal Response (MR) should be reported for patients with relapsed refractory myeloma. When reported, the specific rate of MR should be distinguished from PR or better.
 
MM 27 is a combined Phase I/II study of carfilzomib in combination with panobinostat in the treatment of relapsed/refractory multiple myeloma.
	
 
• Section 7.3.2, 7.3.4, 7.3.5
 
• Section 7.3.3, 7.3.4
 
• Section 7.3.5
 
• Section 7.4
 
• Section 9, Appendix C
 
• Synopsis, Section 10
 

## History of Amendments for MM 27 (continued)

Amd #	Amd Date	Revision(s) Made	Refer to this Section in the Protocol
3	26 March 2013	
If dose level 5 is found to be tolerable, then additional patients will be recruited at this dose level into an expansion cohort of 30 patients for Phase II for a total of 60 Phase II patients (30 patients for dose level 4 and 30 patients for dose level 5). A maximum of up to 80 total patients may be enrolled in this study (including patients from the dose escalation Phase I studies).
 
 
• Patients should receive acyclovir or similar (famciclovir, valacyclovir) anti-varicella (anti-herpes) agent prophylaxis. In addition, patients <del>should</del> may receive antibiotic prophylaxis with ciprofloxacin or other fluoroquinolone (or imethroprim/sulfamethoxazole if fluoroquinolones are contradicted) if clinically indicated.
 
 
Addition to Table 4 Panobinostat and Carfilzomib Dose Level Modifications:
 
Carfilzomib IV. 15mg/m^2, 20mg/m^2, 27mg/m^2, 36mg/m^2, 45mg/m^2, 56mg/m^2
 
MM 27 is a Phase I/Phase II study of carfilzomib in combination with panobinostat in the treatment of relapsed/refractory multiple myeloma. The total number of patients expected to be accrued is up to 5480.
 
The Phase II efficacy objective is to evaluate the overall response in patients with relapsed/refractory multiple myeloma treated at the optimal dose level in the first 4 dose levels established during the Phase I portion, as well as the overall response in patients at dose level 5 if this dose level is found to be tolerable and patients are recruited into the expansion cohort. The response rates in the two dose levels will be evaluated separately.
	
 
• Section 5.3
 
• Section 5.2
 
• Section 6
 
• Synopsis, Section 10.1
 

## History of Amendments for MM 27 (continued)

Amd #	Amd Date	Revision(s) Made	Refer to this Section in the Protocol
3	26 March 2013	Following additions made: Efficacy will be evaluated for patients treated at the optimal dose level from the first 4 dose levels during Phase I together with those entered in the Phase II dose expansion portion of the study, and at dose level 5 (if this dose level is found to be tolerable and patients are recruited into the expansion cohort) . The data from the two dose levels will be evaluated separately, and no formal statistical comparisons will be made between the two dose levels.	

• Section 10.4

## History of Amendments for MM 27 (continued)

Amd #	Amd Date	Revision(s) Made	Refer to this Section in the Protocol
4	24 October 2013	
A parallel Phase I study will occur to evaluate a minimum of 3 patients and a maximum of 6 patients following a standard dose escalation design at additional dose levels of the combination of carfilzomib and panobinostat (see Table 3).
 
If additional dose levels are found to be tolerable, then additional patients will be recruited into an expansion cohort which will be open at all sites - a maximum total of 36 patients (including the ones recruited into the parallel Phase I study) will be treated at this dose level.
 
Dose Level 6 added as follows:            Carfilzomib            Cycle 1 = 20 mg/m^2 IV D1,2/ 56 mg/m^2 IV D 8, 9, 15, 16            Cycle 2 to Progression = 56 mg/m^2 IV D 1, 2, 8, 9, 15, 16            Panobinostat            Cycle 1 = 20 mg D 1, 3, 5, 15, 17, 19            Cycle 2 to progression = 20 mg D 1, 3, 5, 15, 17, 19
 
Window for Holidays and Vacations
 
For holidays and vacations it is preferred to plan ahead and adjust D1 of treatment +/- 48 hours of the cycle the patient plans to be gone for treatment so that the patient follows the treatment schedule per protocol. If it is not possible to adjust D1, the carfilzomib infusion days may be adjusted +/- 48 hours after cycle 1 for a holiday or vacation. There is no window allowed during cycle 1 and for the panobinostat doses except for D1 with the window described above.
 
A parallel Phase I study will occur to evaluate a minimum of 3 patients and a maximum of 6 patients following a standard dose escalation design at additional dose levels of the combination of carfilzomib and panobinostat.
	
 
• Section 5
   
• Table 3
   
• Section 5.1.3
   
• Section 5.2
   
•
 

## History of Amendments for MM 27 (continued)

Amd	Amd Date	Revision(s) Made	Refer to this Section in the Protocol
4	24 October 2013	
If a dose level in the parallel Phase I study is found to be tolerable, then additional patients will be recruited at this dose level into an expansion cohort of 30 patients for Phase II for a total of 60 Phase II patients (including 30 patients for dose level 4), <del>and 30 patients for dose level 5</del>. A maximum of up to 80 total patients may be enrolled in this study (including patients from the dose escalation Phase I studies).
 
At any point in this treatment, patients suspected of PD will have response assessed again to confirm disease progression (i.e. 2 sets of response assessments at least 1 week apart). The outcomes will be reviewed by the study chair before the patient is removed from the study. After the second set of response assessments, if disease progression is confirmed, the date of the first set of response assessments should be recorded as the progression date
 
The Phase II efficacy objective is to evaluate the overall response in patients with relapsed/refractory multiple myeloma treated at the optimal dose level in the first 4 dose levels established during the Phase I portion, <del>as well as</del>. In addition, the overall response in patients at any additional dose level <del>is found to be tolerable and patients are recruited into the expansion cohort</del> will be evaluated.
 
Efficacy will be evaluated for patients treated at the optimal dose level from the first 4 dose levels during Phase I together with those entered in the Phase II dose expansion portion of the study, and at any additional dose level (if this dose level is found to be tolerable and patients are recruited into the expansion cohort).
 
SCRI and SCRI Oncology Research Consortium have been updated to SCRI Development Innovations, LLC (SCRI Innovations) as appropriate.
	
 
• Section 5.3
   
• Section 7.4
   
• Section 10.1
   
• Section 10.4
   
• Global Change
 

## History of Amendments for MM 27 (continued)

Amd	Amd Date	Revision(s) Made	Refer to this Section in the Protocol
5	03 August 2015	Moved hydration and safety guidelines for carfilzomib from Section 6.4	
 
• Section 5.1.2
 

		Deleted duplicate concomitant medication information	
 
• Section 5.4
 

		Added hypertensive events to Table 8	
 
• Section 6.3
 

		Added management guidelines for carfilzomib-related events	
 
• Section 6.4
 

		Amended to refer to the most current carfilzomib Investigator's Brochure.	
 
• Section 8.2.5
 

		Updated precautions and risks for carfilzomib	
 
• Section 8.2.6
 

		Amended response criteria for Progressive Disease as follows: Increase of $\geq 25\%$ from the nadir in at least one of the following criteria:	
 
• Appendix C
 

		
 
• serum M-protein (absolute increase must be <math>\geq 0.5</math> g/dL <del>and absolute value must be <math>\geq 1</math> g/dL</del>)
 
	

## SYNOPSIS

Title of Study:	A Phase I/II Study of the Combination of Panobinostat and Carfilzomib in Patients with Relapsed/Refractory Multiple Myeloma	
Protocol Number:	MM 27	Study Phase: I-II
Study Centers:	Multicentered	
Objectives:	
Primary Objectives:
 
 
• To establish the optimal doses of carfilzomib in and panobinostat that can be administered to patients with relapsed/refractory multiple myeloma. (Phase I)
 
• To evaluate the overall response in patients with relapsed/refractory multiple myeloma treated with the combination of panobinostat and carfilzomib. (Phase II)
 
 
Secondary Objectives:
 
 
• To evaluate time-to-progression (TTP)
 
• To evaluate progression-free-survival (PFS)
 
• To evaluate overall-survival (OS)
 
• To evaluate safety
 
	
Study Design:	
This is an open-label, non-randomized Phase I/II study of patients with relapsed or refractory multiple myeloma.
 
The Phase I study will determine the MTD of the combination of carfilzomib and panobinostat. The Phase I portion will follow a standard dose escalation design, beginning with dose level 1 (see Table 2). Patients will be assessed for dose-limiting toxicity (DLT) at each visit during Cycle 1 prior to receiving treatment. Dose modifications will not be permitted during Cycle 1 unless a patient experiences a DLT (see Section 5.2.2.). Treatment cycles will be administered at 28-day intervals. Panobinostat will be administered orally three times weekly during weeks 1 and 3 of each cycle (Days 1, 3, 5, 15, 17, 19). Carfilzomib will be administered intravenously on Days 1, 2, 8, 9, 15, and 16 of each cycle. During Cycle 1, the carfilzomib dose will be escalated after the Day 2 dose, if well tolerated.
 
A maximum of four dose levels will be evaluated. Approximately 24 patients will be enrolled during the Phase I portion to establish the MTD.
 
In the Phase II portion of this study, patients with relapsed/refractory multiple myeloma will receive treatment with the panobinostat and carfilzomib combination established during Phase I. Patients will be reevaluated for response to treatment after each cycle (4 week). Patients with objective response or stable disease will continue treatment, with subsequent reevaluations every 4 weeks, until disease progression or unacceptable toxicity occurs.
	
Number of Patients:	Up to 80 eligible patients will be treated in this study.	

## SYNOPSIS

Drug Supply:
	
Panobinostat and Carfilzomib for use in the study will be provided to the Sponsor, SCRI Development Innovations, LLC (SCRI Innovations). Panobinostat will be provided to SCRI Innovations by Novartis Pharmaceuticals. Carfilzomib will be provided to SCRI Innovations by Onyx Pharmaceuticals. Supplies will be requested through SCRI Innovations.

Study Drug(s), Schedule, and Mode of Administration:
	
 
Relapsed/Refractory Multiple Myeloma Patient
 
↓
 
 
ENROLLED
 
 
↓
 
 
Phase I
 
N = 24
 
Panobinostat PO TBD TIW Days 1, 3, 5, 15, 17 and 19
 
Carfilzomib IV TBD Days 1, 2 escalating on Days 8, 9, 15, & 16
 
Dose to be determined
 
Treatment cycles will be repeated every 28 days
 
 
↓
 
 
Once the MTD has been determined, up to 30 patients with refractory/relapsed multiple myeloma may enroll in the Phase II portion.
 
 
↓
 
 
Phase II
 
Panobinostat PO TBD Days 1, 3, 5, 15, 17 and 19
 
Carfilzomib IV TBD Days 1, 2 escalating on Days 8, 9, 15, and 16
 
Treatment cycles will be repeated every 28 days
 
Restaging: patients will be restaged every treatment cycle (every 4 weeks). Patients with disease progression or unacceptable toxicity will be discontinued from the study.
 
 
↓
 
 
 
Continue until tumor progression, or until unacceptable toxicity occurs.
 
 
→
 
 
FOLLOW-UP
 
 
 

## SYNOPSIS

Inclusion Criteria:	
 
1. Eligible participants must have multiple myeloma using standard criteria (Appendix B).
 
2. Patients must have measurable disease requiring systemic therapy defined as at least one of the following: 
 
• Serum M-protein <math>\geq 0.5</math> g/dl (<math>\geq 5</math> g/l)
 
• Urine M-protein <math>\geq 200</math> mg/24 hrs
 
• Serum free light chain assay: involved free light chain level <math>\geq 10</math> mg/dl (<math>\geq 100</math> mg/l) provided the serum free light chain ratio is abnormal
 
 
 
3. Must have progressed during or after at least one previous treatment regimen. Patients who have received previous high dose therapy/autologous stem cell transplantation are eligible.
 
4. Eastern Cooperative Oncology Group (ECOG) performance status of 0-2. (see Appendix A).
 
5. Must meet the following laboratory criteria: 
 
• Absolute neutrophil count (ANC) <math>\geq 1000/\mu\text{L}</math>;
 
• Platelets <math>\geq 70,000/\mu\text{L}</math>;
 
• AST or ALT and alkaline phosphatase (ALP) must be <math>\leq 2.5</math> x ULN, or <math>\leq 5</math> x ULN in patients with plasmacytomas of the liver;
 
• Total bilirubin <math>\leq 1.5</math> x the institutional ULN;
 
• Serum creatinine <math>\leq 1.5</math> x ULN or calculated creatinine clearance <math>\geq 50</math> ml/min;
 
• Serum potassium, calcium, magnesium WNL (These may be corrected prior to starting therapy, to make the patient eligible.)
 
 
 
6. Ability to swallow oral medications.
 
7. Baseline MUGA or ECHO must demonstrate left ventricular ejection fraction (LVEF) <math>\geq</math> the lower limit of the institutional limits of normal.
 
8. Male or females <math>\geq 18</math> years of age.
 
9. Female patients must not be of child-bearing potential or must agree to use adequate contraceptive measures.
 
10. Male patients willing to use adequate contraceptive measures.
 
11. Willingness and ability to comply with the trial and follow-up procedures.
 
12. Ability to understand the nature of this trial and give written informed consent.
 

Exclusion Criteria:	
 
1. Currently receiving or have received systemic cancer therapy (chemotherapy, biologic therapy) <math>\leq 21</math> days of initiating study therapy. For patients receiving small molecule targeted therapy, study treatment may begin <math>>21</math> days after last dose or <math>>5</math> half lives of previous treatment, whichever is shorter. Patients must have completed radiation therapy <math>\geq 7</math> days prior to starting study treatment. Patients must have recovered from or come to a new chronic stable baseline from all treatment-related toxicities. Dexamethasone or other high-dose steroid therapy must be stopped <math>\geq 7</math> days prior to starting study treatment.
 
2. Previous treatment with HDAC, DAC, HSP90 or valproic acid for treatment of cancer.
 
3. Requires valproic acid for any medical condition during the study <math>\leq 5</math> days prior to first panobinostat treatment.
 
4. Patient has not recovered from all therapy-related toxicities associated with prior treatments to <math><</math> Grade 2 CTCAE.
 

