#### 1.3.1. Carfilzomib Phase 2 Single Agent Experience

Two Phase 2 clinical studies are ongoing with carfilzomib in multiple myeloma (MM) patients, PX-171-003-A0 (N=46) in relapsed and refractory MM and PX-171-004 (N=39) in relapsed MM. In both studies, patients were treated with 20 mg/m^2 on Days 1, 2, 8, 9, 15, and 16 every 28 days. In these studies there were four cases of suspected or documented tumor lysis syndrome (TLS) prior to institution of the prophylaxis guidelines. Since these guidelines were implemented, no further cases of TLS have been reported. In both studies, the most common adverse events were fatigue, anemia, thrombocytopenia, gastrointestinal, and dyspnea. There were reported cases of increased in serum creatinine that were primarily < Grade 2. A very low rate of treatment-emergent peripheral neuropathy ( 2.2% Grade 3/4), was observed in PX-171-003-A0 despite the fact that 78% of patients had Grade 1/2 neuropathy upon study entry (Jagannath et al. 2009).

Patients in the PX-171-003-A0 study had progressive myeloma and were refractory to their most recent therapy, often including bortezomib and/or an immunomodulatory drug

(usually lenalidomide). In this study, 18% of patients had partial responses, with 7% minor responses and 41% stable disease. The median time to progression on the PX-171-003-A0 study was 5.1 months with duration of response of 7.4 months (Jagannath et al. 2009).

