A “stepped up” dosing schedule, referred to as 20/27 mg/m^2, has subsequently been incorporated into the PX-171-003 study in order to maximize the clinical benefit of carfilzomib. Patients receive 20 mg/m^2 for the first cycle and 27 mg/m^2 thereafter. The study completed enrollment of 266 patients by the end of 2009 and may form the basis for an accelerated approval NDA filing by the end of 2010. To date, this dosing schedule has been well tolerated (Alsina et al. 2007). An independent Safety Oversight Group (SOG) evaluated the safety data from the 40 of 250 patients to be enrolled on the 20/27 schedule and agreed that the trial should proceed without modification. No cases of TLS were observed and rates of BUN and creatinine elevation dropped sharply, with Grade 3/4 renal impairment dropping to 2.2%, most likely due to hydration and very low dose dexamethasone. Treatment-emergent peripheral neuropathy remains low on this portion of the study with 15% Grade 1/2 and one (0.7%) Grade 3/4 event reported to date on PX-171-003-A18. In addition, anemia rates in the PX-171-003-A1 (higher dose) were lower than those reported in the PX-171-003-A0 portion of the study, possibly indicating that the higher dose of carfilzomib is achieving better clearing of neoplastic cells in the bone marrow allowing superior normal marrow reconstitution. Rates of thrombocytopenia and neutropenia were similar in the two cohorts, with Grade 3 neutropenia in ~5% without any Grade 4 neutropenia to date (Jagannath et al. 2009)

In the PX-171-004 study, a first cohort of patients received 20 mg/m^2. The subset of patients (N=54) that had not previously received bortezomib had an overall response rate (ORR) of 46% (2% CR, 9% VGPR and 35% PR), while the bortezomib treated patients (N=33) had an ORR of 18% (3% CR, 3% VGPR and 12% PR) (Wang et al. 2009 and Seigel et al. 2009). The median time to progression (TTP) was 7.6 and 5.3 months in these two groups, respectively.

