## 3. PATIENT ELIGIBILITY AND WITHDRAWAL CRITERIA

### 3.1. Inclusion Criteria

1. Eligible participants must have multiple myeloma using standard criteria (Appendix B).
2. Patients must have measurable disease requiring systemic therapy defined as at least one of the following:
  - Serum M-protein  $\geq 0.5$  g/dl ( $\geq 5$  g/l)
  - Urine M-protein  $\geq 200$  mg/24 hrs
  - Serum free light chain assay: involved free light chain level  $\geq 10$  mg/dl ( $\geq 100$  mg/l) provided the serum free light chain ratio is abnormal
3. Must have progressed during or after at least one previous bortezomib-containing treatment regimen. Patients who have received previous high-dose therapy/autologous stem cell transplantation are eligible.
4. Eastern Cooperative Oncology Group (ECOG) performance status of 0-2. (see Appendix A).
5. Must meet the following laboratory criteria:
  - Absolute neutrophil count (ANC)  $\geq 1000/\mu\text{L}$ ;
  - Platelets  $\geq 70,000/\mu\text{L}$ ;
  - AST or ALT and alkaline phosphatase (ALP) must be  $\leq 2.5$  x ULN, or  $\leq 5$  x ULN in patients with plasmacytomas of the liver;
  - Total bilirubin  $\leq 1.5$  x the institutional ULN;
  - Serum creatinine  $\leq 1.5$  x ULN or calculated creatinine clearance  $\geq 50$  ml/min;
  - Serum potassium, calcium, magnesium WNL (These may be corrected prior to starting therapy, to make the patient eligible.)
6. Ability to swallow oral medications.
7. Baseline MUGA or ECHO must demonstrate left ventricular ejection fraction (LVEF)  $\geq$  the lower limit of the institutional limits of normal.

8. Male or females  $\geq 18$  years of age.
9. Female patients must not be of childbearing potential or must agree to use adequate contraceptive measures.
10. Male patients willing to use adequate contraceptive measures.
11. Willingness and ability to comply with the trial and follow-up procedures.
12. Ability to understand the nature of this trial and give written informed consent.

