### **3.2. Exclusion Criteria**

1. Currently receiving or have received systemic cancer therapy (chemotherapy, biologic therapy)  $\leq 21$  days of initiating study therapy. For patients receiving small molecule targeted therapy, study treatment may begin  $>21$  days after last dose or  $>5$  half lives of previous treatment, whichever is shorter. Patients must have completed radiation therapy  $\geq 7$  days prior to starting study treatment. Patients must have recovered from or come to a new chronic stable baseline from all treatment-related toxicities. Dexamethasone or other high-dose steroid therapy must be stopped  $\geq 7$  days prior to starting study treatment.
2. Previous treatment with HDAC, DAC, HSP90 or valproic acid for treatment of cancer.
3. Requires valproic acid for any medical condition during the study  $\leq 5$  days prior to first panobinostat treatment.
4. Patient has not recovered from all therapy-related toxicities associated with prior treatments to  $<$  Grade 2 CTCAE.
5. Known history of allergy to Captisol® (a cyclodextrin derivative used to solubilize carfilzomib).
6. Patients with pleural effusions requiring thoracentesis or ascites requiring paracentesis  $\leq 14$  days prior to study entry.
7. Patients using medications that have a risk of prolonging the QT interval or inducing Torsade de Pointes if treatment cannot be discontinued or switched to a different medication prior to receiving study drug (see Appendix F).
8. Patients with  $>$  grade 2 diarrhea.
9. Patients with impaired cardiac function, including any of the following conditions:
  - History or presence of sustained ventricular tachyarrhythmia.
  - Any history of ventricular fibrillation or Torsade de pointes.
  - Bradycardia defined as HR  $< 50$  bpm. Patients with pacemakers are eligible if HR  $\geq 50$  bpm.
  - Screening ECG with a QTc  $> 450$  msec.
  - Right bundle branch block + left anterior hemiblock (bifascicular block).
  - Patients with myocardial infarction or unstable angina  $\leq 6$  months prior to starting study drug.

- Other clinically significant heart disease (e.g. CHF NY Heart Association class III or IV (Appendix D), uncontrolled hypertension, history of labile hypertension, or history of poor compliance with an antihypertensive regimen).
10. Infection requiring IV antibiotics.
  11. Patients with > grade 2 peripheral neuropathy or with uncontrolled pain.
  12. Women who are pregnant or lactating.

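### The synopsis and Section 3.1 disagree on whether prior bortezomib is required; if bortezomib-naive patients enrol, the comparison with the 18% null rate is likely biased towards success

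*Combined protocol and SAP*

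**What the plan says.** Criterion 3 in the synopsis inclusion list reads "Must have progressed during or after at least one previous treatment regimen". Criterion 3 in Section 3.1 reads "Must have progressed during or after at least one previous bortezomib-containing treatment regimen". Both are complete sentences in current text.

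The amendment history shows that criteria were at times revised in both places together. Amendment 1 cites "Synopsis, Section 3.2 Exclusion Criteria #4" and Amendment 2 cites "Synopsis, Section 3.1, #2". No entry mentions criterion 3. Section 4 routes enrolment through the sponsor but does not say which list is checked.

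Section 10.1, repeated in the synopsis, sets the Phase II comparison: a historical carfilzomib response rate of about 18%, a target of 36%, 27 patients, 80% power, and a one-sided test at 0.10. It does not name the source of the 18%. Section 10.4.1 plans the response rate with 95% confidence intervals and gives no threshold for success. Section 10 has no cap, stratification or subgroup by prior bortezomib.

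Section 1.3.1 gives the relevant single-agent results. In PX-171-004, patients who "had not previously received bortezomib had an overall response rate (ORR) of 46" per cent, and the "bortezomib treated patients (N=33) had an ORR of 18" per cent. In PX-171-003-A0, 18% had partial responses; those patients were "refractory to their most recent therapy, often including bortezomib and/or an immunomodulatory drug".

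**The concern.** A patient who progressed after a regimen without bortezomib, and never had one with it, is eligible under the synopsis and ineligible under Section 3.1. In a single-arm trial, eligibility is the main thing that makes a fixed historical rate a fair null. By the protocol's own account, single-agent response differs by 28 percentage points with prior bortezomib (46% against 18%), and the naive rate alone exceeds the 36% that the trial would count as a doubling. If naive patients are admitted and the null stays at 18%, part of any excess could be case mix, with no contribution from panobinostat.

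**Working it through.** **Reproducing the plan's figure.** Inputs from Section 10.1: n = 27, null 0.18, alternative 0.36, one-sided alpha 0.10. With X binomial, find the smallest k with P(X ≥ k | 27, 0.18) ≤ 0.10.

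- k = 7: P = 0.200, too large.
- k = 8: P = 0.098, acceptable.
- Power at k = 8: P(X ≥ 8 | 27, 0.36) = 0.812.

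The stated 27 patients and 80% power are reproduced. The arithmetic is sound; the question is which population the 18% describes. The cut-off of 8 of 27 is inferred from Section 10.1, since the plan states none.

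**Effect of case mix.** Suppose panobinostat adds nothing. Let f be the naive share (not given in the documents), r the single-agent response rate in naive patients, and 0.18 the rate in the rest. The expected response rate is

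p = f × r + (1 − f) × 0.18.

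For f = 0.25 and r = 0.46: p = 0.25 × 0.46 + 0.75 × 0.18 = 0.115 + 0.135 = 0.25.

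The false-positive rate is P(X ≥ 8 | 27, 0.25) = 0.357. Fixing the counts at 7 naive and 20 treated patients, instead of a random mix, gives 0.365.

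**Sensitivity to the naive rate.** 46% of 54 is about 25 responders, and the exact 95% interval for 25/54 is 33% to 60%. At the lower end, p = 0.25 × 0.33 + 0.75 × 0.18 = 0.2175, and P(X ≥ 8 | 27, 0.2175) = 0.218.

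| Naive share | Naive rate | Expected rate, no panobinostat effect | P(≥ 8 of 27) |
|---|---|---|---|
| 0 | any | 18% | 0.098 |
| 25% | 33% | 21.75% | 0.22 |
| 25% | 46% | 25% | 0.36 |

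**Sensitivity to the treated rate.** 18% of 33 is 6 responders, exact 95% interval 7% to 35%. Keep f = 0.25 and let the treated rate run over that interval. With the naive rate held at 46%, adding naive patients raises P(≥ 8 of 27) by 0.07 to 0.27. With the naive rate at its lower limit of 0.326, the change runs from −0.02 to +0.12. The negative values occur only where the treated rate is at the top of its interval and exceeds the naive rate. An upward bias is therefore likely but not certain.

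**The case against.** The strongest reply is that the two lists are nested. Everyone who meets Section 3.1 also meets the synopsis, so a site applying both enrols only patients who progressed on or after bortezomib. Bias needs someone to work from the synopsis alone. The synopsis also lags the body elsewhere: it still speaks of a maximum of four dose levels and up to 30 Phase II patients, where Sections 5 and 5.3 have further levels and 60. A missing qualifier in a summary is a plausible explanation. This lowers the probability of harm, but no text gives either list precedence, so the contradiction stands.

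The inputs are also weak. The 18% has two candidate sources, and neither is shown to match Section 3.1: one group was bortezomib-treated, which is not the same as having progressed on or after it, and in the other prior bortezomib was only frequent. Both rates come from small groups at 20 mg/m², whereas dose levels 4 to 6 step up to 45 or 56 mg/m². Section 1.3.1 also disagrees with itself on the size of PX-171-004: N = 39 in one place, subsets of 54 and 33 (87 together) in another. These points limit the illustration to an indication of scale.

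Three stronger readings are not supported. A reader might infer that naive patients were enrolled; nothing shows this. A reader might take 0.36 as the trial's actual error rate; it rests on an assumed share, assumed rates and an inferred cut-off. A reader might conclude that the primary comparison must be restricted to patients with prior bortezomib. That would change the Section 10.4 population after enrolment in an open-label trial and cost power: if 25% of 27 were naive, about 20 would remain, needing at least 7 responses, with power 0.62 against 0.81.

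**Conclusion.** The contradiction is certain and should be corrected. Its effect on the primary endpoint is conditional: if bortezomib-naive patients enter, the comparison with 18% is likely biased towards success, because the protocol's own single-agent rate for them is well above 18%. At a 25% naive share the chance of wrongly passing 8 of 27 goes from 0.10 to about 0.36, or to about 0.22 if the naive rate is 33%. With no naive patients, this source adds nothing. The size rests on a naive share that the documents do not give, a success threshold that Section 10.4.1 does not state, and historical rates from small groups at a lower carfilzomib dose whose reported size is inconsistent. The direction follows from 46% against 18% and would fail only near the limits of both intervals.

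**What to change.** 1. Reconcile criterion 3 so that the synopsis and Section 3.1 read the same.
2. In Section 10.1, state which study and population the 18% comes from, so that the eligible population and the null rate match, and resolve the conflicting sizes given for PX-171-004 in Section 1.3.1. If bortezomib-naive patients are intended, restate the reference rate and the sample-size statement for that population.
3. If naive patients have already enrolled, report the response rate with its confidence interval by prior bortezomib as a supportive analysis beside the planned one. The planned analysis and its power stay as they are.

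The first two items are a one-line correction and short source statements; re-sizing arises only if the intended population includes naive patients. The third is one extra table.

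The same edit can settle a separate mismatch in exclusion 11, where only Section 3.2 extends the criterion to "grade 2 peripheral neuropathy or with uncontrolled pain". It has no bearing on this bias.
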